# Flow diagram for randomized, controlled trial

## 6.0 Enrollment/Randomization

40 school age children and youth with ASD will be recruited through local community agencies (e.g., schools, churches, and rehabilitation centers), social media platforms (e.g., Facebook and Reddit) and direct contact. Participants will be divided into 2 groups based on their age such as, group 1: 7-14 years and group 2: 15-22 years. Co-PI will allocate participant based on the coin flip such that heads = intervention group and tails = control group. The next participant in the same age range (range 1: 7-14 years, range 2: 15-22 years) will be assigned to the other group.

The process will continue till there are 10 participants in each age range for each intervention and control group (total n = 40).

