# 3.0 Outcome Measures/Endpoints

# 3.1 Primary Outcome Measures:

- 1. High resolution pressure mat: Static balance will be objectively measured using an HR Mat pressure mat (Tekscan Inc.). The center of pressure will be measured at 100Hz using the center of pressure coordinates by inbuilt software. The area of the postural sway and direction of the sway will be measured as indicators of static balance with participants standing on the pressure mat with hands at their side under 2 conditions: eyes open and eyes closed for 30 seconds each condition. A member of the research team will stand beside the participant and provide balance support as needed.
- 2. Qualisys Motion Capture system: Step length, stride length, step-width, double support period, cadence and velocity are the gait parameters that will be measured as indicators of dynamic balance using Qualisys motion capture system. The

Qualisys motion capture system will be used to assess gait as a measure of dynamic balance. The system is composed of 13-infrared cameras that capture light reflected by passive markers at a frequency of 100 Hz. It is a reliable and a valid tool for gait assessment. The biomechanical model of feet will be constructed using Visual 3D software for gait analysis. Participants will wear the same sneakers/sports shoes for each assessment. Nine markers will be placed bilaterally (18 total) at the following points: distal aspect of the great toe, 1st metatarsal, 5th metatarsal, top of the foot, medial malleolus, and lateral malleolus, proximal heel, distal heel, and lateral heel. A comfortable walking speed for each participant will be recorded using a stopwatch to measure the time it takes them to walk back and forth on a 15-meter-long-platform 3 times and the average of the 3 trials will be calculated. Participants will then walk at the same speed at least 5 times or until the entire gait cycle is captured by the infrared camera system twice. Gait cycle is defined as heel-strike to heel strike on the dominant foot. A couple of practice trials will be performed to ensure understanding of the procedure and verbal prompting will be used to remind the participant to walk typically. Biomechanical models of feet will be constructed using Visual 3D software for gait analysis. If the participant is unable to perform this assessment as described, it will be rescheduled up to two times before study dismissal.

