# 5.0 Study Design

Single blinded randomized controlled clinical trial design will be used. After obtaining the consent material, potential participants will be screened using inclusion and exclusion criteria, ASSQ and screening questionnaire. Co-PI will create and administer the assignments. Participants will be blinded to the allocation process to either the intervention or the control group.

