# 7.0 Study Procedures

1. Prior to day 1: Informed consent materials, a screening questionnaire, and Autism Spectrum Screening Questionnaire (ASSQ) will be sent electronically to parents/caregivers. Participants and parents/caregivers in both groups will be given access to a video of the data collection space, intervention space setting, and a short introduction of the research personnel for review. If the participants are 18 years or older, this information will be shared with the participants directly and they will fill the questionnaires. If the participant is less than 18 years old, the information will be shared with the parent/legal guardian to be completed. Additionally, The ASSQ is a commonly used valid and reliable 27-item checklist to be filled in by parent/caregiver for assessing symptom characteristics of ASD. The ASSQ can be completed in 10 minutes using a 3-point Likert scale with possible score range being 0 of 54 with 19 being a cut off for a parent/caregiver rating identifying ASD. This tool will be used as a part of demographic screening of the participants prior to the pre-intervention day and used to better describe individual autism symptoms than is available in a medical or educational diagnosis. The researcher will subsequently contact participants and parent/caregiver to review the information, check for understanding, (particularly the terminology used in the ASSQ), assess eligibility via screening tool and address any other questions prior to study inclusion and visit.

Study participation will require 9 visits: 1 pre-intervention visit, 6 intervention visits, 1 post-intervention visits and 1 retention visit. Participants will receive \$10 Amazon or Kroger gift card after completing each session with total possible compensation of \$90.

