# 2. Pre-intervention/session 1:

2.1 As part of familiarization, participants will be shown and allowed to handle the different data collection instruments and ask questions. The intervention group will be shown the Nintendo Switch to get familiarized with their operation and functions. Parents/caregivers of the participants (under 18 years of age) in the intervention group will be handed over the Nintendo Switch Sports

to be connected at their home for the duration of intervention. Participants 18 years of age or older will be given the device. Researchers will provide any technological assistance required for this purpose.

2.2 Weight will be recorded using a calibrated scale and height measured using a stadiometer. The Edinburgh Handedness Inventory-short form (EHI-SF) will be used to assess hand-preference. It is a valid and reliable 4-item checklist of everyday tasks and participants score their hand preference on 5-point Likert scale (for each item, always right= 100, usually right= 50, usually left= 50, always left= -100). A researcher will read the rating scale to those with low literacy level. Handedness will be determined using a laterality quotient. The laterality quotient is interpreted as left handers (-100 to -61), mixed handers (-60 to +60) and right handers (61 to 100). Hand length will be calculated using a tape cloth, measured from greater tuberosity to distal end of middle digit on the right hand and leg length iliac crest to ground on the right leg.

Participants will be shown the different data collection instruments to handle, get familiarized and ask questions. Participant's hand dominance will be recorded using the Edinberg Handedness Inventory-short form. Participant's foot dominance will be recorded by asking them to kick an imaginary ball placed on the ground in front of them. Practice trials for balance and gait assessments will be conducted to ensure understanding of the protocol. Baseline assessments for posture and gait will be performed.

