	pping while walking, frequent falls, uses support while walking or standing unsupported?  Yes (1)
	No (2)
	If yes, please specify: (3)
Q1	1 Does participant currently play any video games?
0	Yes (1)
	No (2)
0	If yes, specify the gaming consoles: (3)
Q1	2 What the frequency of playing the video games?
	3 Does participant currently play active video games (which involves participant moving his dy to move the avatar on the screen)?
0	Yes (1)
0	No (2)
0	If yes, what is the frequency and average duration: (3)

Q14 Does participant currently have access to Nintendo Switch Sports (2022) game  O Yes (1)  O No (2)	e?
Q15 Does participant have any other challenges that may limit their ability to engage study such as will he/she be able to engage in video game activity for 10 minutes with distracted?	=
	<del>-</del>
Q16 Will the participant need any individualized motivation such as visual schedul sticker chart, etc. for engaging in this research? Please specify:	e, checklist,
	_

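### Each coin flip also settles the next same-age allocation, so at least 20 of 40 assignments are predictable, with no concealment from enrolling staff described and the arm apparently visible before baseline

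*Combined protocol and SAP*

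**What the plan says.** Section 6.0 states the rule in two sentences: "Co-PI will allocate participant based on the coin flip such that heads = intervention group and tails = control group", and then "The next participant in the same age range (range 1: 7-14 years, range 2: 15-22 years) will be assigned to the other group". This continues until each of the two age ranges (7-14 and 15-22 years) has 10 participants per arm, 40 in total.

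On who handles allocation, section 5.0 says "Co-PI will create and administer the assignments". Its only blinding statement is "Participants will be blinded to the allocation process to either the intervention or the control group".

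On enrolment, section 7.0, step 1, has the researcher contact families to "assess eligibility via screening tool and address any other questions prior to study inclusion and visit". The plan does not say whether this person is the Co-PI, or whether they are kept unaware of earlier arms.

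On Session 1, step 2.1 of section 7.0 says "The intervention group will be shown the Nintendo Switch to get familiarized with their operation and functions" and has the console handed over to that group. The baseline assessments come afterwards, in steps 2.2 to 2.4.

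Two safeguards are described in section 3.1, item 3: a different researcher records the Pediatric Balance Scale (PBS), and rater reliability is checked from video. That researcher is not said to be unaware of the arm.

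**The concern.** Random allocation protects the comparison only if those who decide who enters, and when, cannot foresee the arm. Here the rule itself discloses the next arm after every flip, and no barrier is described between the assignments and the person who screens.

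Some room for judgement exists:

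- The criteria on following instructions and on severe behaviours (section 4) are not purely mechanical.
- Screening item Q15 asks about "any other challenges that may limit their ability to engage", and its example is ten minutes of video gaming, which only one arm will do.
- For the gait test, section 3.1 says: "If the participant is unable to perform this assessment as described, it will be rescheduled up to two times before study dismissal". If the arm is already known at Session 1, that decision is made with knowledge of it.

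Two kinds of bias are possible. If selection acts on the level of balance, the planned group main effect (section 11.0) is biased but the group-by-time interaction is not. If selection acts on capacity to improve, or if knowledge of the arm influences the baseline PBS score, the interaction is biased. Sway and gait are instrumented and so less exposed to scoring bias. No analysis can restore concealment after enrolment.

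**Working it through.** **The plan's own total.** 2 age ranges × 2 arms × 10 = 40, as stated. Each age range has 20 participants.

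**Predictable assignments** = 2 × (20 − flips per age range).

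- One flip per pair: 2 × (20 − 10) = 20 of 40 (50%). Expected correct guesses: 20 + 20/2 = 30 of 40 (75%).
- One flip per age range, then alternation: 2 × (20 − 1) = 38 of 40 (95%). Expected correct guesses: 38 + 2/2 = 39 of 40.

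These counts apply to someone who knows the previous same-age arm.

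**Size of a possible bias (assumed inputs).** The plan gives no figures for this. Assume 20 per arm, three visits with SD 1 and equal correlation ρ of 0.5 or 0.8, no true effect, and participants in acted-on predictable slots who differ by 0.25 SD. The expected difference between arms is d = 0.25 × (share of slots predictable) × (share of those acted on) × (2 if in opposite directions by arm, 1 if in one direction).

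- Pairs, all acted on, both directions: 0.25 × 0.5 × 2 = 0.25 SD. Half acted on, or one direction only: 0.125 SD. A quarter, both directions: 0.0625 SD.
- Alternation, same cases: 0.25 × 0.95 × 2 = 0.475 SD; about 0.24 SD; about 0.12 SD.

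Type I error at p ≤ 0.05 in the planned two-way mixed ANOVA, from 20,000 simulated trials per setting (ρ = 0.5 / 0.8):

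| Case | Stable shift: group main effect | Shift in response: interaction |
|---|---|---|
| Pairs, all, both directions | 15.0 / 12.9% | 10.8 / 22.0% |
| Pairs, half, both directions | 7.5 / 7.0% | 6.7 / 8.9% |
| Pairs, all, one direction | 7.7 / 6.7% | 6.9 / 8.6% |
| Pairs, quarter, both directions | 5.3 / 5.3% | 5.4 / 6.1% |
| Alternation, all, both directions | 43.6 / 34.8% | 30.5 / 66.7% |
| Alternation, half, both directions | 14.6 / 12.6% | 10.4 / 20.0% |
| Alternation, all, one direction | 14.8 / 12.9% | 11.1 / 20.5% |
| Alternation, quarter, both directions | 7.5 / 6.9% | 6.2 / 8.3% |

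With no shift, both tests reject in 4.7-5.1% of trials. Under any stable shift the interaction stays at 4.7-5.4%.

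**Cross-check by noncentral F** for d = 0.25:

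- Group main effect: λ = (40 × 0.25²/4) × 3/(1 + 2ρ) = 0.94 (ρ = 0.5) or 0.72 (ρ = 0.8), on 1 and 38 df. Error 15.7% or 13.1%.
- Interaction, with the difference present at visits 2 and 3 only: λ = (40 × 0.25²/4) × (2/3)/(1 − ρ) = 0.83 or 2.08, on 2 and 76 df. Error 11.5% or 22.6%.

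Both agree with the simulation.

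**Arm-aware scoring of the baseline PBS.** If scores are lower in the intervention arm by 0.25 SD, the interaction rejects in 11.5 / 22.4% of trials. At 0.10 SD it rejects in 5.8 / 7.4%.

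**Would other block sizes alone help?** Even for a guesser who knows the block sizes and all past arms, correct guessing is 70.8% with blocks of 4, and 69.3% with two blocks of 4 and two of 6 in random order. The present rule gives 75% under pairs.

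**The case against.** The strongest reply is that the harm is hypothetical. Under the pairs reading, which the wording about the process continuing makes the more natural one, the scheme is age-stratified blocking of size 2. Each participant still has an even chance of either arm, and the second of a pair is predictable only to someone who knows the first. The documents support neither the 0.25 SD shift nor any share of slots acted on. The interaction, which tests differential change, is untouched by a stable shift, and biasing it through selection requires staff to foresee who will improve.

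Several lesser points also carry weight. Most screening items are yes/no survey answers, including the one on severe behaviours. Q15 asks about engaging in the study generally, with gaming as its example. Rescheduling of the gait test has a fixed limit. The step order in Session 1 is loose, since step 2.2 repeats instrument familiarization, and the calendar's familiarization entry names neither the console nor an arm. The flow diagram and some pages are not available.

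What stands is that the error rates are conditional, the alternation figures need the less natural reading, and disclosure before baseline is an inference. The objection does not remove the rule itself. One role always knows the previous arm, and the available text describes nothing that keeps it from the person who screens. The group main effect is a planned test, so a stable shift matters.

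**Conclusion.** The concern holds and should be corrected before further enrolment. With high confidence, the stated rule makes at least 20 of 40 assignments (38 under strict alternation) known to anyone who knows the previous same-age arm, and the available text describes no concealment from enrolling staff.

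Disclosure of the arm before baseline is probable from the order of the Session 1 steps, but is not stated.

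The size of the bias is unknown. Under the assumptions above and the pairs reading, type I error ranges from about 5% when few predictable slots are acted on, to 13-15% for the group main effect or 11-22% for the interaction in the strong case. Alternation would be worse. These rates illustrate what could happen; they are not estimates of what will.

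**What to change.** Concealment comes first:

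1. Generate the sequence by computer in advance within the two existing age strata, keeping 10 per arm per stratum.
2. Have it held in sealed opaque envelopes or a locked file by a team member with no part in recruitment, screening or assessment.
3. Reveal each assignment only after eligibility is confirmed and the Session 1 baseline, including any rescheduled gait assessment, is complete.
4. Move the console demonstration and handover to the end of Session 1.
5. State that the separate PBS recorder is not told the arm at Sessions 1, 8 and 9.

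As a secondary step, replace the coin rule with permuted blocks of undisclosed, varying size, for example two of 4 and two of 6 in random order per stratum. This adds little without concealment. At the very least, section 6.0 should say whether the coin is flipped once per pair or once per age range.

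The cost is protocol wording, a short program for the list, and 40 envelopes or a locked file. No extra visits are needed. No extra staff are needed if one existing team member is independent of recruitment, screening and assessment, which the documents do not establish. With blocks of up to 6, a stratum that stops early could be out of balance by up to 3, against 1 under the present rule.

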# 7.0 Study Procedures

1. Prior to day 1: Informed consent materials, a screening questionnaire, and Autism Spectrum Screening Questionnaire (ASSQ) will be sent electronically to parents/caregivers. Participants and parents/caregivers in both groups will be given access to a video of the data collection space, intervention space setting, and a short introduction of the research personnel for review. If the participants are 18 years or older, this information will be shared with the participants directly and they will fill the questionnaires. If the participant is less than 18 years old, the information will be shared with the parent/legal guardian to be completed. Additionally, The ASSQ is a commonly used valid and reliable 27-item checklist to be filled in by parent/caregiver for assessing symptom characteristics of ASD. The ASSQ can be completed in 10 minutes using a 3-point Likert scale with possible score range being 0 of 54 with 19 being a cut off for a parent/caregiver rating identifying ASD. This tool will be used as a part of demographic screening of the participants prior to the pre-intervention day and used to better describe individual autism symptoms than is available in a medical or educational diagnosis. The researcher will subsequently contact participants and parent/caregiver to review the information, check for understanding, (particularly the terminology used in the ASSQ), assess eligibility via screening tool and address any other questions prior to study inclusion and visit.

Study participation will require 9 visits: 1 pre-intervention visit, 6 intervention visits, 1 post-intervention visits and 1 retention visit. Participants will receive \$10 Amazon or Kroger gift card after completing each session with total possible compensation of \$90.

# 2. Pre-intervention/session 1:

2.1 As part of familiarization, participants will be shown and allowed to handle the different data collection instruments and ask questions. The intervention group will be shown the Nintendo Switch to get familiarized with their operation and functions. Parents/caregivers of the participants (under 18 years of age) in the intervention group will be handed over the Nintendo Switch Sports

to be connected at their home for the duration of intervention. Participants 18 years of age or older will be given the device. Researchers will provide any technological assistance required for this purpose.

2.2 Weight will be recorded using a calibrated scale and height measured using a stadiometer. The Edinburgh Handedness Inventory-short form (EHI-SF) will be used to assess hand-preference. It is a valid and reliable 4-item checklist of everyday tasks and participants score their hand preference on 5-point Likert scale (for each item, always right= 100, usually right= 50, usually left= 50, always left= -100). A researcher will read the rating scale to those with low literacy level. Handedness will be determined using a laterality quotient. The laterality quotient is interpreted as left handers (-100 to -61), mixed handers (-60 to +60) and right handers (61 to 100). Hand length will be calculated using a tape cloth, measured from greater tuberosity to distal end of middle digit on the right hand and leg length iliac crest to ground on the right leg.

Participants will be shown the different data collection instruments to handle, get familiarized and ask questions. Participant's hand dominance will be recorded using the Edinberg Handedness Inventory-short form. Participant's foot dominance will be recorded by asking them to kick an imaginary ball placed on the ground in front of them. Practice trials for balance and gait assessments will be conducted to ensure understanding of the protocol. Baseline assessments for posture and gait will be performed.

2.3 Dynamic balance assessment: Dynamic balance will be assessed as previously described using Qualisys motion capture system and dynamic components of PBS. The biomechanical model of feet will be constructed using Visual 3D software for gait analysis. Participants will wear the same sneakers/sports shoes for each assessment. Nine markers will be placed bilaterally (18 total) at the following points: distal aspect of the great toe, 1st metatarsal, 5th metatarsal, top of the foot, medial malleolus, and lateral malleolus, proximal heel, distal heel, and lateral heel. A comfortable walking speed for each participant will be recorded using a stopwatch to measure the time it takes them to walk back and forth on a 15-meter-long-platform 3 times and the average of the 3 trials will be calculated. Participants will then walk at the same speed at least 5 times or until the entire gait cycle is captured by the infra-red camera system twice. Gait cycle is defined as heel-strike to heel strike on the dominant foot. A couple of practice trials will be performed to ensure understanding of the procedure and verbal prompting will be used to remind the participant to walk typically

2.4 Static balance assessment: Static balance will be assessed as previously described using pressure mat and static components of PBS. The area of the postural sway and direction of the sway will be measured as indicators of static balance with participants standing on the pressure mat with hands at their side under 2 conditions: eyes open and eyes closed for 30 seconds each condition. A member of the research team will stand beside the participant and provide balance support as needed.

# 3. Intervention/ session 2-7:

Session 2 will occur 3-5 days after the baseline assessment.

3.1: Intervention group: Participants will choose 2 interactive video games on the Nintendo Switch Sports from golf, Frisbee, beach tennis, soccer, Volleyball, badminton, bowling, and chambara. The researcher will supervise the sessions via zoom. These games address motor learning principles as follows. First, they cause movement of the body's center of pressure in mediolateral, anteroposterior-, and diagonal directions without the participant paying active attention to the directional changes, leading to implicit and explicit learning. Second, they display the score achieved by the participant during- and after- each game leading to the participant having knowledge of the performance and the results. Third, playing 2 games provides task and training variability.

Games will be played for 10 minutes each with a 5-minute break in between. The same 2 games will be played each session. Participants will stand at least 3 meters away from the TV while playing the games. Verbal prompts /motivators will be provided during the games. Each session will take approximately 40 minutes. The caregivers will be present at one-hands distance from the participant to prevent any falls. Additionally, participants will be asked to place a chair at a reachable distance which they can hold on to prevent falls. Ideally, each session will occur with an off day in between, however this may not be realistic depending on participant and caregiver schedules and so sessions will occur at participant/caregiver convenience.

Control group: Control group participants will receive balance instruction from the researcher at home via Zoom. The following standard balance exercises will be performed for 15 minutes with 5 minutes of warm and cool down each. Breaks will be given as per the participants' need and verbal prompts/motivators provided. The caregivers will be present at one-hands distance from the

participant to prevent any falls. Additionally, participants will be asked to place a chair at a reachable distance which they can hold on to prevent falls.

Warm up exercises: Neck flexion-extension, shoulder flexion-extension, shoulder abduction-adduction, shoulder clockwise rotation, elbow flexion-extension, hip flexion-extension, hip abduction-adduction, knee flexion-extension, ankle plantar flexion- dorsi flexion, trunk flexion-extension. All exercises will be done by standing holding the back of a chair for 5 repetitions bilaterally.

Balance exercises: Standing with feet together for 10 seconds 5 times, standing with 1 foot in front of other for 10 seconds 5 times on both sides, standing on one leg for 10 seconds 5 times on both sides, walking with one foot in front of other on a 1-meter-long line for 5 repetitions and standing on a balance board for 30 seconds for 3 repetitions.

Cool down exercises: Stretching of calf muscles, quadriceps, hamstrings, lateral trunk flexors, truck extensors, shoulder abductors, shoulder adductors for 10 seconds each for 5 repetitions bilaterally. All stretches will be done by standing holding the back of a chair whenever necessary.

